Fear of hypoglycemia (FoH) is becoming an important barrier to achieving good glycemic control in patients with type 2 diabetes. Clinical care professionals have been working to address FoH in patients with diabetes mellitus, and the behaviour change wheel (BCW) theory, which states that individuals must possess the three behavioral components of ability, opportunity, and motivation in order to develop behavioral change, helps interventionists analyze the behavioral components that are lacking in order to determine the focus of the intervention, and then select the most appropriate intervention based on the combination of the nine functions of the intervention and implement it. The purpose of this study was to develop a health education intervention program based on the BCW theory to reduce the level of fear of hypoglycemia in patients with type 2 diabetes and to investigate the feasibility, acceptability, and preliminary effects of the program.

5. Research purpose

The purpose of this study was to develop a health education intervention program based on the BCW theory to reduce the level of fear of hypoglycemia in patients with type 2 diabetes and to investigate the feasibility, acceptability, and preliminary effects of the program.

6. Inclusion and Exclusion Criteria

Inclusion criteria: (1) Compliance with the 2020 Chinese guidelines for the prevention and treatment of type 2 diabetes mellitus patients^[24]; (2) Age ≥ 18 years; (3) Duration of diabetes mellitus ≥ 1 year; (4) According to the elevated item endorsement criterion (EI criterion): Hypoglycaemic Fear-Worry Scale (HFS-WS) Any item ≥ 3 points was judged as FoH; (5) Have the ability to listen, read, write and walk, and be able to cooperate with the completion of the study; (6) Have a smart phone, and be able to use WeChat or phone to communicate proficiently; (7) Voluntarily participate in this study and sign the informed consent form. Exclusion Criteria: (1) Those who are combined with acute complications or other serious diseases or disorders of consciousness, such as diabetic hypertonic state, tumour, coma, etc.; (2) Those who are combined with psychiatric diseases or taking psychotropic drugs. (3) Patients who have recently or are

participating in other studies on similar topics.

7. Intervention process

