From August 2021 to January 2022, T2DM patients who met the inclusion and exclusion criteria were selected from 2 tertiary hospitals in Yangzhou City. The control group implemented conventional diabetes health education, and the intervention group implemented health education based on BCW theory on top of the control group.

8. Sample size estimation

According to the formula for calculating the sample content: $n_1=n_2=2[(Z_{\alpha}+Z_{\beta}) \sigma/\delta]^2$, n_1 , n_2 are the required sample contents of the two groups, set $\alpha=0.05$, $\beta=0.1$, check the boundary table $Z_{\alpha/2}=1.96$, $Z_{\beta}=1.282$. $n_1=n_2 \approx 22$ cases according to the sample size estimation formula of the pre-experimental results substituted into the comparison of the two sample means, considering a 15% attrition rate, expert opinion and clinical situation, 25 patients in each group were finally determined.

9. Randomisation

Participants were identified through screening of medical records and face-to-face interviews, and participants signed a written consent form to participate in the study. After the baseline assessment, participants were randomly assigned to either the intervention or control group using a lottery method after drawing a labelled card in an opaque sealed envelope from an independent research assistant who was not involved in the recruitment and implementation of the study.

10. Measurement index

General information questionnaire: admission day 1; hypoglycaemia fear scale (primary indicator): admission day 1, 4 weeks post intervention, 8 weeks post intervention; impaired hypoglycaemia awareness score (secondary indicator): admission day 1, 4 weeks post intervention, 8 weeks post intervention; medical support scale (secondary indicator): admission day 1, 4 weeks post intervention, 8 weeks post intervention; diabetes self-management attitude scale (secondary indicator). Day 1 of admission, 4 weeks post-intervention, 8 weeks post-intervention.

11. Ethical consideration

The study was ethically approved by the Ethics Committee of the College of Nursing

of Yangzhou University (YZUHL20210088).

12. Statistical analysis of data

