SPSS 26.0 software was applied for data analysis. Describing the general demographic characteristics of the study population: Mean \pm standard deviation ($\pm s$) was used to describe measures that conformed to normal distribution, and median and interquartile spacing M (QR) were used to describe skewed distribution; count data were expressed as frequencies and constitutive ratios. Homogeneity test: the chi-square test or Fisher's exact test was used for the count data of the two groups at baseline, non-parametric test was used for the rank count data, and t-test or non-parametric test was used for the measurement data. Repeated measures ANOVA was used to analyse the intervention effect of each indicator within groups, and two independent samples t-test was used to compare between groups at different time points before and after the intervention. The significance level $P < 0.05$ indicated that the difference was statistically significant.

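### Section 12 labels a within-group ANOVA as the test of the intervention effect and does not say that the planned between-group t-tests decide

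*Combined protocol and SAP*

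**What the plan says.** Section 12 gives two analyses of the outcome scales in one sentence. The first is "Repeated measures ANOVA was used to analyse the intervention effect of each indicator within groups". The second is "two independent samples t-test was used to compare between groups at different time points before and after the intervention". It then sets a single threshold: "The significance level $P < 0.05$ indicated that the difference was statistically significant". It states no group-by-time term, baseline adjustment, primary time point, or rule on which of the two analyses answers the trial's question.

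Four other sections bear on this:

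- **Section 6** makes a raised fear score an entry condition: "Hypoglycaemic Fear-Worry Scale (HFS-WS) Any item ≥ 3 points was judged as FoH".
- **Section 7** describes the arms: "The control group implemented conventional diabetes health education, and the intervention group implemented health education based on BCW theory on top of the control group".
- **Section 9** makes this a randomised comparison: "participants were randomly assigned to either the intervention or control group using a lottery method".
- **Section 10** names the fear scale as the primary indicator, measured on admission day 1 and at 4 and 8 weeks.

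Section 8 sizes the trial on a between-group contrast: "according to the sample size estimation formula of the pre-experimental results substituted into the comparison of the two sample means".

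**The concern.** In Section 12, the words that name the intervention effect are attached to a test of change over time within an arm. Randomisation gives that test no protection, because anything that lowers scores in both arms counts as effect.

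Two such influences are built into the design:

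- Patients enter because at least one worry item is high. Scores selected for being high tend to fall when measured again.
- Both arms receive conventional diabetes education, so some improvement is expected even if the added programme does nothing.

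A reader who follows Section 12 literally could take a significant fall in the intervention arm as the intervention effect, or could contrast a significant intervention arm with a non-significant control arm. Either could happen when the randomised comparison shows no difference. Investigating preliminary effects is a stated aim in Section 5, so this bears on one of the study's own conclusions.

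**Working it through.** **1. The plan's own figure.** Section 8 uses n = 2[(Zα + Zβ)σ/δ]² with 1.96 and 1.282, giving about 22 per group. Neither σ nor δ is stated, so the 22 can only be inverted: δ/σ = √(2 × 3.242² / 22) = √(21.02 / 22) ≈ 0.977. Allowing for 15% attrition, 22 / 0.85 = 25.9, or 26, against the stated 25. That gap of one patient is immaterial here. Completers expected from 25 are 25 × 0.85 = 21.25, so 21 per arm is used below. The formula compares two groups, so the trial was sized on the between-group test.

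**2. Inputs for the false-positive check.**

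- From the documents: three measurement times, two randomised arms, α = 0.05, and entry on a raised fear item.
- Assumed, because the documents give no figures: scores are normal, a fraction q of screened patients qualifies on a total score, the test-retest correlation is ρ, and the score used for entry is also the baseline. The central case is q = 0.5 and ρ = 0.6. The ranges are q = 0.3 to 0.7 and ρ = 0.5 to 0.8.

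**3. Size of the fall with no treatment effect.** If the top fraction q of a standard normal score is selected, the expected fall on re-measurement is (1 − ρ) × φ(z)/q, where φ is the normal density and z is the cut-off.

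- Central case: 0.4 × 0.399 / 0.5 ≈ 0.32 SD.
- Mildest case (q = 0.7, ρ = 0.8): about 0.10 SD.
- Strongest case (q = 0.3, ρ = 0.5): about 0.58 SD.

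**4. How often each analysis is significant when the programme does nothing.** Simulation with 21 per arm and a one-way repeated measures ANOVA in each arm:

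| Result | Central case | Over the ranges |
|---|---|---|
| Intervention-arm ANOVA, P < 0.05 | about 39% | about 10% to 83% |
| Intervention arm significant, control not | about 24% | at most about 25% |
| Between-group t-test, one time point | about 5% | about 5% |
| Either post-baseline t-test | 8% to 10% | 8% to 10% |

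The second row can be checked by hand. The arms are independent, so the rate is 0.39 × (1 − 0.39) ≈ 0.24. The product p(1 − p) cannot exceed 0.25, which gives the upper limit.

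**5. Second model.** Suppose instead that both arms fall by the same amount after baseline, from any cause (25 per arm, correlation 0.5 to 0.7). The intervention-arm ANOVA is then significant in 16% to 23% of trials for a 0.2 SD fall, 30% to 48% for 0.3 SD and 71% to 91% for 0.5 SD. With no common fall it stays at 5%. The group-by-time interaction and a baseline-adjusted ANCOVA stay at about 5% throughout.

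**6. Effect of the actual entry rule.** Section 6 selects on any single item, not on a total. Assuming 13 items with inter-item correlation 0.4, half qualifying and ρ = 0.6, the intervention-arm rate drops from about 39% to about 28%.

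**The case against.** The strongest reply is that a valid test is already in the plan. The t-tests appear in the same sentence as the ANOVA, the arms are randomised and concurrent, and the sample size rests on comparing two means. Regression to the mean and the benefit of conventional education cancel between arms, so each t-test holds about 5%. This stands. A reader might infer that the within-group ANOVA is the trial's only test of efficacy, or that the trial cannot yield a valid result. The documents support neither.

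A reader might also infer that significance in one arm alone will be reported as efficacy. No section says so: Section 12 only sets the level at which a difference is called significant. The fault is that nothing in the plan rules that reading out.

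On size, counting every trial in which exactly one arm is significant gives about 47% in the central case (2 × 0.39 × 0.61 ≈ 0.48, within rounding). That total includes trials in which only the control arm is significant, which nobody would take as support for the programme. The relevant pattern is about 24%.

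Three further limits stand:

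- The documents do not say whether the primary fear scale is the worry subscale or a wider total.
- They do not say that screening and baseline are the same administration.
- Entry selection acts directly on the fear scale only, not on the three secondary indicators.

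Finally, a pilot is not confirmatory. That lowers the stakes, but the plan still tests for effects and needs to say which test counts.

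**Conclusion.** The point holds in a limited form. Section 12 gives the name of intervention effect to an analysis that cannot isolate it, and leaves the valid between-group comparison without decisive status. Under no treatment effect, the mislabelled test is significant in about 39% of trials in the central case and about 10% to 83% over the assumed ranges. Selection on single items would bring these figures down, and benefit from conventional education would push them up. Even the mildest case is twice the nominal 5%.

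The qualifying fraction, the correlation and the normal total score are assumptions, so the percentages show scale and do not predict this trial. The conclusion that within-arm change mixes programme effect with common change does not depend on them.

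This is a should-fix, not a must-fix, because the planned t-tests already provide a valid randomised comparison at each time point.

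**What to change.** Replace the sentence on repeated measures ANOVA and t-tests in Section 12 with:

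> The intervention effect is the between-group difference. The primary analysis compares groups on the hypoglycaemia fear scale at one pre-named post-intervention time point (4 or 8 weeks), adjusted for the admission-day-1 score (ANCOVA or a baseline-adjusted mixed model), with 95% CI and P value. The other time point and the other scales are analysed the same way as secondary. Within-group changes are descriptive only, with no claim of effect.

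Both the baseline adjustment and the single time point matter. A mixed model with only group, visit and their interaction would, with complete data, return the same 4- and 8-week differences as the planned t-tests. It would also leave the 8% to 10% error from accepting either visit.

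The cost is wording. No new data or larger sample is needed. At 22 per group, with the implied effect of 0.977 SD and an assumed correlation of 0.5 to 0.7, simulated power is 88% to 89% for the t-test and 95% to 99% for ANCOVA. The sponsor gives up within-group P values and must commit to one primary time point.

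### The plan expects 15% attrition but defines no analysis set or missing-data handling, and its between-group result rests on separate unadjusted t-tests among those who attend each visit

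*Combined protocol and SAP*

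**What the plan says.** Section 8 (Sample size estimation) arrives at about 22 patients per arm and raises this for expected losses: "considering a 15% attrition rate, expert opinion and clinical situation, 25 patients in each group were finally determined". The 15% is a single figure, not split by arm, visit or pattern.

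Section 10 (Measurement index) sets three measurements of the primary outcome: "hypoglycaemia fear scale (primary indicator): admission day 1, 4 weeks post intervention, 8 weeks post intervention". The three secondary scales follow the same schedule. Section 9 places randomisation after the baseline assessment, so every randomised patient should have a baseline score.

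Section 12 (Statistical analysis of data) gives the whole analysis of effects: "Repeated measures ANOVA was used to analyse the intervention effect of each indicator within groups, and two independent samples t-test was used to compare". The t-tests set one arm against the other, separately at each visit. On software it says only "SPSS 26.0 software was applied for data analysis"; it names no procedure and no missing-data option. Neither this section nor any other defines an analysis population, an imputation method, a likelihood-based model or a sensitivity analysis.

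**The concern.** The sponsor foresees missing outcomes and enlarges the sample for them. A larger sample protects power. It does not protect the comparison against dropout that is related to arm or outcome.

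The two named methods also treat an incomplete patient differently by default. Classical repeated measures ANOVA needs a full row per patient, whereas a t-test at one visit needs only that visit's score. A patient seen at 4 weeks but not at 8 would be in the 4-week t-test and out of the ANOVA. With nothing written down, the handling could be chosen after the data have been seen.

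The between-group t-tests also make no use of the baseline score, although every randomised patient should have one, and they treat the two follow-ups as unrelated.

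What is at stake is the main result on preliminary effect: a group difference among attenders, tested at P < 0.05, that may not describe the groups as randomised.

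**Working it through.** **Inputs.** Section 8: about 22 per arm before attrition, 15% attrition, 25 per arm (50 in total), quantiles 1.96 and 1.282. Section 10: baseline, 4 weeks and 8 weeks. Section 12: within-group ANOVA and a t-test at each time point.

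**1. The plan's own figure.** Dividing by the retained fraction: 22 / 0.85 = 25.9. Multiplying up: 22 × 1.15 = 25.3. The stated 25 is reproduced within rounding. The base of 22 cannot be checked, because the effect and SD from the pre-experiment are not given. Solving 22 = 2[(1.96 + 1.282)σ/δ]² gives δ/σ = 0.977.

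**2. What 15% attrition leaves.** 25 × 0.85 = 21.25 per arm; 50 × 0.85 = 42.5 in total. At δ/σ = 0.977 the normal-approximation power is 93.3% with 25 per arm, 90.0% with 22 and 89.0% with 21.25. Power is not the problem.

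**3. Who enters each analysis by default.** The documents give no missingness pattern, so these three are assumptions that show the range (patients out of 50):

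| Assumed pattern | t-test, baseline | t-test, 4 weeks | t-test, 8 weeks | ANOVA (all three scores) |
|---|---|---|---|---|
| A. Monotone dropout: 7.5% gone by week 4, 15% by week 8 | 50 | 50 × 0.925 = 46.25 | 50 × 0.85 = 42.5 | 42.5 |
| B. 15% miss one follow-up: half week 4 only, half week 8 only | 50 | 46.25 | 46.25 | 42.5 |
| C. 15% miss each follow-up, independently | 50 | 42.5 | 42.5 | 50 × 0.85² = 36.1 |

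The ANOVA would rest on about 36 to 42 patients and the follow-up t-tests on about 42 to 46. In pattern A the ANOVA and the 8-week t-test use the same patients. If everyone who leaves does so before week 4, the 4-week set coincides with them too. Pattern C is the extreme: 1 − 0.85² = 28% are incomplete, nearly double the plan's single 15%.

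**4. Where bias in the group difference could arise.** Section 12 gives the ANOVA to change within groups and all between-group comparison to the t-tests. Deletion in the ANOVA therefore cannot move the group difference; only absence from the t-tests can. If a fraction p of an arm is missing, and those present differ from those missing by g on average, the mean of those present differs from the full-arm mean by p × g. The error in the group difference is p × g in the intervention arm minus p × g in the control arm. Section 8 gives one overall rate and nothing on g, so neither sign nor size can be derived.

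**The case against.** The strongest reply is that the plan is silent and prescribes nothing wrong. A reader might infer from section 12 that incomplete patients are to be deleted from the ANOVA and kept in the t-tests. No sentence says so; that is how the methods behave by default. If missing scores were imputed, both analyses would cover everyone randomised. If dropouts were removed throughout, the sets would match, though they would not be the full randomised set. This reply stands as to wording. It does not remove the gap, because the plan must say which of these applies.

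Three stronger readings are tempting, and the documents do not support them:

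- **That the ANOVA and the two follow-up t-tests must describe three different patient sets.** Under monotone dropout the ANOVA and 8-week sets are identical, and the baseline comparison covers everyone randomised.
- **That the plan throws away 4-week data and so biases the group difference.** The 4-week t-test would use all scores observed at that visit, and the ANOVA makes no between-group comparison.
- **That the more demanding arm will lose its poor responders, favouring the intervention.** If 15% of that arm were lost, would have scored 0.8 SD worse than those who stay, and no such loss occurred among controls, the shift would be 0.15 × 0.8 = 0.12 SD. The 0.8 SD and the one-sided loss are both assumptions. The same loss in both arms gives zero, and the same loss among controls only gives 0.12 SD the other way. The intervention tables put the 60-minute lectures inside the hospital stay and make the post-discharge contacts mainly 15 minutes weekly by WeChat or telephone. Extra contact could just as well improve retention.

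It can also be said that this is a pilot, with feasibility and acceptability among its aims. That carries limited weight: the study is sized for 90% power and tests its effects for significance.

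**Conclusion.** The point holds as a gap in specification together with a weak choice of between-group method. The plan anticipates 15% attrition over two follow-ups, defines no analysis set or missing-data handling, and rests the group comparison on separate t-tests among attenders without baseline adjustment.

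The ANOVA counts assume that the methods run on their defaults: about 42 of 50 if the plan's 15% is the total incomplete, and about 36 only if that rate applies independently at each follow-up. Bias in the group difference is possible where dropout relates to arm or response; it is not demonstrated, and the documents give nothing from which to size it. Loss of power is not part of the point. The change should be made before analysis, because it is cheap and settles in advance a choice that is otherwise open once data are seen.

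**What to change.** In section 12, define the analysis set as all randomised patients in the arm to which they were assigned, whatever sessions they attended.

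Make the between-group analysis of each scale one mixed model for repeated measures: REML, unstructured covariance, baseline score as covariate, and group, visit and group-by-visit terms. Use every observed 4- and 8-week score and report the group difference at each visit. With two post-baseline visits the unstructured covariance has three parameters, which is feasible with 50 patients.

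The model assumes missing at random and gains nothing from a patient with no follow-up score. Add one sensitivity analysis by multiple imputation, for example reference-based on the control arm, and state how missing scores in both arms are filled. Filling one arm with a single mean would understate the uncertainty.

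The cost is a revised paragraph in section 12 and a little more analysis work. The mixed model runs in the SPSS already named, and no new data are needed. The downside is that the main analysis relies on missing at random, which the sensitivity analysis is there to probe.

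### The between-group t-tests ignore the admission day 1 score: the comparison is valid, but baseline adjustment would narrow the interval and correct for chance imbalance at almost no cost

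*Combined protocol and SAP*

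**What the plan says.** Section 12 of the combined protocol and SAP names one between-group method for the outcomes: "two independent samples t-test was used to compare between groups at different time points before and after the intervention". The same sentence gives the longitudinal method a different job: "Repeated measures ANOVA was used to analyse the intervention effect of each indicator within groups". For balance at baseline, the section plans homogeneity tests, and for scale scores "t-test or non-parametric test was used for the measurement data". It does not say what follows if such a test is significant. Section 12 specifies no ANCOVA, change score, mixed model or group-by-time contrast.

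Section 10 schedules every scale at baseline and at two follow-ups:
- For the primary scale: "hypoglycaemia fear scale (primary indicator): admission day 1, 4 weeks post intervention, 8 weeks post intervention".
- The three secondary scales keep to the same pattern. One entry reads "impaired hypoglycaemia awareness score (secondary indicator): admission day 1, 4 weeks post intervention, 8 weeks post intervention", and the scales for medical support and for attitude to self-management have matching time points.

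Section 9 sets the order of events: "After the baseline assessment, participants were randomly assigned to either the intervention or control group using a lottery method". It describes no stratification. Section 8 sizes the trial on a plain comparison of two means.

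**The concern.** A participant's own day 1 score on a scale is usually the best available predictor of the later score on that scale. Here it is measured before allocation, so it is a legitimate covariate and needs no extra data. Leaving it out of the between-group comparison has two consequences:
- Variation between participants that baseline could explain stays in the error term, so the interval is wider than it need be.
- If the lottery happens to leave the arms apart on the scale, part of that gap carries through into the observed follow-up difference.

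Neither the design nor the analysis deals with the second consequence. Allocation is not stratified, and the homogeneity tests detect only large gaps and trigger no correction. In a pilot this small, whose aims include preliminary effects, the estimate and its interval are the main output that a later trial would use.

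**Working it through.** **Inputs from the documents.** Two-sided alpha 0.05 (1.96), beta 0.1 (1.282), about 22 per group before attrition, 15% attrition, 25 per group (all Section 8).

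**Inputs not in the documents.** Delta, sigma and the baseline to follow-up correlation r. I assume r = 0.3 / 0.5 / 0.7, with r = 0 as the worst case, and use 0.6 SD as an assumed smaller effect.

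**Step 1: the plan's own figure.** Section 8 uses n = 2[(Zα/2 + Zβ)σ/δ]². Without delta and sigma, 22 can only be solved backwards: δ/σ = (1.96 + 1.282) × √(2/22) = 0.977. Allowing for attrition gives 22/0.85 = 25.9, or 26, against 25 stated; that difference does not matter here. Evaluable per arm: 25 × 0.85 = 21.25, taken as 21.

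**Step 2: unadjusted t-test, 21 per arm.**
- SE = √(2/21) = 0.3086 SD.
- 95% CI half-width = t(40) × SE = 2.021 × 0.3086 = 0.624 SD.
- Power (noncentral t): 87.1% at 0.977 SD; 47.5% at 0.6 SD.

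**Step 3: ANCOVA, 21 per arm.** The residual variance is multiplied by 1 − r². The price of estimating the slope is one degree of freedom (39 left) and, on average, a variance factor of 1 + 1/(2n − 4) = 1 + 1/38.
- SE = √[(2/21)(1 − r²)(1 + 1/38)].
- Half-width = t(39) × SE, with t(39) = 2.023.

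| r | SE (SD) | Half-width (SD) | Change in half-width | Power at 0.977 SD | Power at 0.6 SD |
|---|---|---|---|---|---|
| t-test | 0.309 | 0.624 | – | 87.1% | 47.5% |
| 0 | 0.313 | 0.632 | +1% | 86.2% | 46.5% |
| 0.3 | 0.298 | 0.603 | −3% | 89.2% | 50.1% |
| 0.5 | 0.271 | 0.548 | −12% | 94.1% | 58.0% |
| 0.7 | 0.223 | 0.452 | −28% | 99.0% | 74.6% |

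The half-widths break even where 0.632 × √(1 − r²) = 0.624, that is, at r of about 0.16.

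**Step 4: chance imbalance, 25 per arm.**
- SD of the baseline mean difference = √(2/25) = 0.283 SD.
- P(gap of 0.3 SD or more) = P(|Z| > 0.3/0.283) = 0.289.
- Smallest gap that a baseline t-test calls significant: t(48) × √(2/25) = 2.011 × 0.283 = 0.57 SD.
- Shift in the unadjusted follow-up difference from a 0.3 SD gap = 0.3r = 0.09 / 0.15 / 0.21 SD, which is 9% / 15% / 21% of 0.977 SD.

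**Step 5: simulation, 22 per arm, 20,000 trials for each r.** Over all trials the t-test is unbiased and its type I error is 4.9% to 5.2%. Among trials with a baseline gap above 0.3 SD, its type I error is 6.9% / 8.9% / 12.4% at r = 0.3 / 0.5 / 0.7, against about 5% for ANCOVA.

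**The case against.** The strongest reply is that nothing is broken. A reader might infer from this point that the t-test is biased or that its P values are wrong. The documents do not support that: participants are randomised, so over all allocations the t-test is unbiased and holds its 5% level, and its standard error already allows for chance imbalance. What remains is lost precision, plus an error conditional on the imbalance actually observed.

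A reader might also infer that the day 1 score is used nowhere except in the homogeneity tests. That goes too far. Section 10 lists day 1 as the first of three time points, so on the natural reading it also enters the repeated measures ANOVA. Because that analysis is described as looking at effects within groups, it gives no adjusted contrast between the arms. The mention of an intervention effect leaves some room for a two-group model with a group-by-time term, but this is the weaker reading and no such term is stated.

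Third, the benefit depends on a correlation that the documents do not give. Section 6 admits only patients scoring at least 3 on some HFS-WS item. This may restrict the baseline range and lower r on the primary scale. At r = 0.3 the gain is small. This caution stands, so no large gain in power can be promised.

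Finally, this is a pilot, and 0.98 SD is back-solved rather than stated, so power is not the main consideration. That is fair, but Section 12 tests at P < 0.05 and preliminary effects are a stated aim, so a narrower interval is still worth having.

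**Conclusion.** The point holds as a near-free improvement, not as an error that invalidates the analysis. The planned between-group comparison does not use a pre-randomisation covariate that the trial already collects on every scale. With 21 evaluable per arm and assumed r from 0.3 to 0.7, adjustment narrows the 95% CI by 3% to 28%. It raises power from 87% to between 89% and 99% at the back-solved 0.98 SD, and from 48% to between 50% and 75% at an assumed 0.6 SD. It also removes the expected carry-through of a chance baseline gap, which is 0.09 to 0.21 SD for a gap of 0.3 SD. If r were zero, the loss would be about one point of power.

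These sizes rest on the assumed r, a linear relation with a common slope, equal variances, and attrition at the planned 15%. The direction of the gain needs only r above about 0.16.

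**What to change.** In Section 12, replace the follow-up t-tests with ANCOVA for each scale at 4 and at 8 weeks: follow-up score = group + that scale's own admission day 1 score. Report the adjusted mean difference between arms with its 95% CI at each time point. State that repeated measures ANOVA remains a within-group description, if that is what is meant.

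The cost is one sentence in the plan and one degree of freedom per model. No new data are needed, because the baseline assessment already precedes randomisation. The change should be made before outcomes are examined by arm.

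Showing baseline characteristics without P values is an optional reporting change. It does not affect the treatment estimate.
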